2.1 The research questions

- To what extent do each of the five items in the WAT correlate to the patient's disease status?
- How do patients and clinicians feel about using the WAT?

2.2 Outline of the project

It is widely recognised that patient-reported outcomes give a measure of overall effect of clinicians' actions on patients and that they can be used to guide the management of the patient's condition (1-4). They can also have an empowering effect as the patient may feel that they are agents, and not just subjects, in their treatment pathway (5, 6). In the case of advanced and metastatic prostate cancer (i.e. cancer which has spread from the prostate to distant sites, the clinical means of assessing how the patient's disease is responding to treatment (Level of PSA [prostate specific antigen, produced normally in the prostate but also produced in prostate cancer cells], and radiological/magnetic scans) are somewhat imperfect as they do not take into account the impact on the patient's life and his response and reaction.

The Wolverhampton Assessment Tool (copy attached) is an objectively analysed, reproducible clinical assessment tool, developed from validated clinical study tools and piloted and refined with patient and clinician feedback to produce a simple 5-item questionnaire which asks patients how they feel normally in terms of pain, urinary frequency, eating, and tiredness. Patients are also asked to pick from a list the single statement which best represents them normally. The working hypothesis is that the patient's scores and his chosen statement correlate with the current state of his disease (7) and indicate whether the current treatment regimen needs clinician intervention.

The Tool allows assessment of the patient's disease status without him always needing to attend hospital and hence reduces potential exposure to Covid-19 for both patient and hospital staff. See attached *Oncology Interim Prostate Cancer Patient Management Guidelines* Royal Wolverhampton Hospital, March 2020 (8)

The aims of the present project are to:

- 1 evaluate how the Tool and the patient's clinical status correlate
- 2 examine patient and clinician attitudes to using the Tool

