2.3 How the research will be conducted

In the light of the COVID-19 pandemic, oncologists at New Cross Hospital are advised to consider using the Tool (as per the *Oncology Interim Prostate Cancer Patient Management Guidelines* (8)) as a means of home monitoring of patients. The present project intends to provide robust evidence as to the clinical usefulness of Tool as well as insights into the drivers and barriers to its use by patients and clinicians.

This is a mixed-method study, incorporating both quantitative and qualitative elements. As such, it is both objective and subjective:

- a) It is subjective in that, in using the Wolverhampton Assessment Tool, the patient selects his response to each question on the basis of how he *feels* normally
- b) It is objective in that the tools to be used in the analysis of the quantitative data [i.e. statistical tests such as Mann Whitney-U, Spearman Rank Correlation etc.] are independent of the person using them
- c) Determining clinically the patient's disease status employs objective measures such as PSA, size, distribution and type of metastasis, frequency of night-time urination etc. as well as the clinician's professional judgment which contains both objective and subjective elements (9, 10)
- d) The researchers are not mirrors but they are rather prisms and hence the entire study from conception to analysis and report is a refraction of their experiences

The first phase of the research is a full pilot of the Wolverhampton Assessment Tool in New Cross Hospital, Wolverhampton. Patients who agree to use the Tool to self-monitor their aspects of their health will be invited to consent to share with the researchers their anonymised data from the Tool as well as linked, anonymised clinical data. The frequency of collection of data will be at the discretion of the clinician. Participating patients and clinicians will be invited to take part in a short, semi-structured interview on their experience of using the Tool. All patient data will be treated anonymously, and none linked back to the patient or to their clinician/s.

Clinicians will be asked to record any reasons given by patients who decline to use the Tool.

The clinical data sought on patients will include:

- a) Age
- b) Stage of cancer at diagnosis in terms of the primary tumour, and any presence of disease in lymph nodes and bones
- c) Current stage of cancer in terms of the primary tumour, and any presence of disease in lymph nodes and bones

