- d) Level of PSA – prostate specific antigen, produced normally in the prostate but also produced in prostate cancer cells.
- e) Co-morbidities
- f) Current and previous treatments

The main outcome of the first phase will be to refine, as necessary, both the Tool and the research instruments as well as to establish proof of principle of the clinical utility of Tool.

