2.5 How the data will be analysed

Quantitative data will be analysed by means of statistical tests such as Mann Whitney-U, Spearman Rank Correlation etc. using SPSS v.26. Qualitative data will be analysed using thematic analysis and the constant comparative method.

2.6 The ethical considerations involved in this project.

Patients and clinicians will be asked if they wish to opt into the study and be required to give their explicit consent, both for sharing data and, if they accept to volunteer, for interviews.

All patient data will be anonymised prior to its being shared with the researchers. Recording and notes of interviews will be anonymised. Only the research team will have access to any raw data. All data will be held in a manner that prevents any linking of it back to either the patient or their clinician.

All data held will be anonymous and will be held on a secure University or NHS server. Only the research team will have access to any raw data. All data will be held in a manner that prevents any linking of it back to either the patient or their clinician.

Participants will be given a participant information sheet, which will detail the risks and benefits of participating and of their right to refuse participation or withdraw from the research at any time.

2.7 References.

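### The planned correlation and group-comparison analyses do not show how often a reassuring form accompanies active disease, which is what the stated use of the Tool depends on

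*Protocol*

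**What the plan says.** On use, section 2.2 asserts that "The Tool allows assessment of the patient's disease status without him always needing to attend hospital". The working hypothesis in the same section has two parts: that the scores and the chosen statement correlate with disease state, and that they "indicate whether the current treatment regimen needs clinician intervention". Section 2.3 says "The present project intends to provide robust evidence as to the clinical usefulness of Tool", and closes by giving the main outcome of the first phase as refining the Tool and research instruments and to "establish proof of principle of the clinical utility of Tool".

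On analysis, the quantitative question in 2.1 is "To what extent do each of the five items in the WAT correlate to the patient's disease status". The quantitative aim in 2.2 is to "evaluate how the Tool and the patient's clinical status correlate". Section 2.5 says: "Quantitative data will be analysed by means of statistical tests such as Mann Whitney-U, Spearman Rank Correlation etc. using SPSS v.26".

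The protocol defines no reassuring or concerning form, no category of active disease, and no interval between form and clinical assessment. The form in the 2.8 Appendix has a totals field but no rule for reading it.

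**The concern.** The second part of the working hypothesis is a yes/no use: does this man's form say that a clinician should act? The claim about attendance rests on the same reading. For such a use the key error is a reassuring form from a man whose disease is active. The question and aim in the protocol address only the first part of the hypothesis, the correlation. An analysis that followed them faithfully could report a clear correlation and still say nothing about that error. The decision use, and with it the utility outcome of the first phase, would remain untested when the later phases in 2.4 take the Tool to other oncologists and then to a public app.

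**Working it through.** The protocol states no sample size, target correlation, cut-off or accuracy target, so there is no figure to reproduce. All inputs below are assumptions chosen for illustration.

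**1. One correlation, many miss rates.** Assume 200 men, 60 with active disease and 140 without, and a form read as reassuring or concerning. Let TP and FN be the men with active disease whose forms are concerning and reassuring, and FP and TN the same for men without. For two binary variables Spearman's rho equals

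(TP × TN − FP × FN) / √(60 × 140 × (TP + FP) × (FN + TN)).

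| TP | FN | FP | TN | rho | Active men missed, FN/60 | Reassuring forms with active disease, FN/(FN + TN) |
|---|---|---|---|---|---|---|
| 60 | 0 | 66 | 74 | 4440/8850 = 0.50 | 0% | 0/74 = 0% |
| 39 | 21 | 21 | 119 | 4200/8400 = 0.50 | 35% | 21/140 = 15% |
| 21 | 39 | 1 | 139 | 2880/5735 = 0.50 | 65% | 39/178 = 22% |

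The correlation is the same to two decimals in all three tables, while the miss rate runs from 0% to 65%.

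**2. Graded scores.** Assume that score and disease severity are bivariate normal with correlation r, that 30% of men are active, and that the worst-scoring fraction f is flagged as concerning. Then

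miss rate = [(1 − f) − P(score below its cut and severity below its cut)] / 0.30.

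For r = 0.5 and f = 0.30 the joint probability is 0.5568, so the miss rate is (0.70 − 0.5568)/0.30 = 48%. For r = 0.5 and f = 0.50 it is 0.4216, giving (0.50 − 0.4216)/0.30 = 26%.

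| r | Missed if 30% flagged | Missed if 50% flagged |
|---|---|---|
| 0.3 | 57% | 36% |
| 0.5 | 48% | 26% |
| 0.7 | 36% | 15% |

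The result depends on the flagging rate as well as on the correlation, and the protocol sets no flagging rule.

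**3. Mann-Whitney.** This test compares the two score distributions and corresponds to an area under the curve (AUC). Under a binormal model with equal variances, the miss rate at a given specificity is Φ(Φ⁻¹(specificity) − √2 × Φ⁻¹(AUC)). With AUC 0.80, √2 × Φ⁻¹(0.80) = 1.190. At specificity 0.50 the miss rate is Φ(0 − 1.190) = 12%; at specificity 0.90 it is Φ(1.282 − 1.190) = 54%. Without a cut the test gives no miss rate.

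**4. Precision of the added estimate.** For a 95% interval of half-width h around a sensitivity Se, the number of men with active disease is 1.96² × Se(1 − Se)/h². With Se = 0.80 and h = 0.10 this is 3.84 × 0.16/0.01 = 61.5, so 62 men, or 62/0.30 = 207 in total if 30% are active. Detecting a correlation of 0.3 with 80% power at two-sided 5% takes about 85 men: ((1.960 + 0.842)/atanh(0.3))² + 3. A study of that size would therefore give a wide interval for the miss rate.

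**The case against.** Several points stand against a stronger reading.

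- A reader might infer that the study is confined to correlation. The methods list is open: "statistical tests such as Mann Whitney-U, Spearman Rank Correlation etc". The analysis plan is not at hand and could hold a cross-tabulation. This stands as far as methods go. It does not reach the research question and aim, which are protocol content and give an analysis plan no reason to count false reassurance.
- A reader might infer that the study could never answer the question. The documents do not support that. Tool scores and clinical data are to be linked (2.3), so the limit lies in the stated question and named tests, not in the data.
- A reader might infer that the Tool replaces hospital assessment, or that men with low scores go unseen. Section 2.2 says only that the patient need not always attend, and 2.3 reports that oncologists are advised to consider the Tool. How it is to be read alongside other information may be in the hospital guideline that the protocol cites.
- A reader might infer that a significant correlation would trigger the later phases. No rule in the protocol ties progression to any result.
- The first phase is a pilot, and refinement is its first-named outcome. This lowers the precision that can be asked for, but the same section also promises robust evidence.
- The modelled miss rates depend on the assumed flagging rate. This is true, and so they are given as a range. The three tables make the argument without that model.

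**Conclusion.** The point holds as a mismatch between claim and analysis. The protocol asserts, or sets out to support, a use that depends on reading an individual form correctly, but its quantitative question, aim and named tests address only association and group separation. Those statistics do not determine the miss rate: at a Spearman correlation of about 0.50 it can be anywhere from 0 to 39 of 60 men with active disease (assumed 200 men, 60 active). Under the bivariate-normal model with 30% active, it ranges from 15% to 57% over correlations of 0.3 to 0.7 and flagging rates of 30% and 50%. These figures show what the planned statistics leave open. They are not estimates of how the Tool performs, and nothing in the protocol shows that it misses patients. The matter should be put right before the Tool is taken beyond the first phase, but it does not invalidate the pilot.

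**What to change.** 1. **Add the cross-tabulation.** Extend the first aim in 2.2 and the analysis in 2.5 to include a table of reassuring versus concerning forms against disease status, from the linked data. Before the data are seen, the investigators should fix:
   - the cut for each item and for the form as a whole, noting that in the 2.8 Appendix the activity item runs the opposite way to the four symptom items, with 10 the best state;
   - the definition of active disease, built from the clinical data and clinician judgment that 2.3 already names;
   - the time window that pairs a form with an assessment, since 2.3 leaves collection frequency to the clinician.

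   Report the proportion of men with active disease who gave a reassuring form, and the proportion of reassuring forms with active disease, each with a 95% interval, as descriptive pilot estimates.

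2. **Match the claim to the evidence.** Reword the attendance sentence in 2.2 as a hypothesis. State that correlation alone supports association with disease status, not assessment in place of attendance.

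The cost is a change of wording, one further analysis, and some work to agree the status definition and the window. No new data items are needed beyond the dates that pair form and assessment. The intervals will be wide if few men have active disease, and the resulting claim may be less favourable.

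### Phase 1 is to show clinical utility, but the listed data and the form record neither home completion, nor attendance, nor later unplanned care, so they support only correlation and acceptability

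*Protocol*

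**What the plan says.** Section 2.2 gives the rationale in the indicative: the Tool lets disease status be assessed "without him always needing to attend hospital and hence reduces potential exposure to Covid-19 for both patient and hospital staff". The same section calls it a working hypothesis that the scores and the chosen statement follow the state of the disease and "indicate whether the current treatment regimen needs clinician intervention". It then sets two aims: to "evaluate how the Tool and the patient's clinical status correlate" and to "examine patient and clinician attitudes to using the Tool". The research questions in section 2.1 have the same scope.

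Section 2.3 refers to a hospital guideline that advises oncologists to consider the Tool for monitoring patients at home. It continues: "The present project intends to provide robust evidence as to the clinical usefulness of Tool". The main outcome of phase 1 is to refine the Tool and the research instruments and to "establish proof of principle of the clinical utility of Tool".

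The clinical data listed in section 2.3 are age, stage at diagnosis, current stage, PSA, co-morbidities, and current and previous treatments. How often data are collected is left to the clinician. The form in section 2.8 has an office-use line for totals, date, treatment, cycle and day.

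**The concern.** There are two mismatches.

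First, the 2.2 sentence takes as settled what aim 1 is meant to test. The Tool can spare a visit only if its scores reflect disease status, and that is still a hypothesis two sentences earlier.

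Second, the conclusion promised in 2.3 is wider than the data listed to support it. Usefulness and utility, read with the stated rationale, concern a form completed away from hospital that lets a clinician do without some attendances. Nothing listed identifies such forms or shows what followed them. Under the protocol as written, every form could be completed in clinic, and a reader of the phase 1 report could not tell.

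What is at stake is the step from phase 1 to the later phases in section 2.4, which take the Tool to oncologists across the region and then to app stores. A statement that utility has been shown in principle would carry weight there. If it rests on correlations and interviews alone, it says more than was observed.

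**Working it through.** The protocol gives no sample size, expected correlation, cut-off or event rate on this point, so there is no figure to reproduce. The check sets what is claimed beside what is recorded.

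| Statement | Where | What would be needed to support it | Listed? |
|---|---|---|---|
| Scores relate to disease status | 2.1, 2.2 aim 1 | Tool scores, stage, PSA | Yes |
| Patients and clinicians accept the Tool | 2.1, 2.2 aim 2 | Interviews, reasons for declining | Yes |
| Disease status can be assessed with fewer attendances | 2.2 rationale | Place of completion; whether the form stood in for an attendance | No |
| Lower Covid-19 exposure | 2.2 rationale | At the least, attendances | No |
| Clinical usefulness or utility in home use | 2.3 | The home and attendance items above, and what followed | No |

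Counting the items:

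- Listed clinical data (section 2.3): six items. Those that record attendance: 0. Those that record unplanned care, admission or death: 0.
- Office-use line (section 2.8): five entries. Those that record place of completion: 0. Those that record whether a visit was replaced: 0. Cycle and day place a form within a course of treatment, but they do not say whether it was completed at home or in clinic.

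The first two rows are the study's two aims, and the listed data serve them. The last three rows go beyond the aims, and no listed item serves them.

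An SAP could not close this gap. It could specify separate reporting of home forms, but only if the form showed which ones they were.

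Timing also matters. Section 2.6 has patient data anonymised before sharing and held so that they cannot be linked back. Anything not abstracted before that step would be hard to add later.

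**The case against.** The strongest reply is that reduced attendance is background. It is not a research question, an aim or a named outcome, and the sentence in 2.2 leads straight to an existing hospital guideline. On that view, asking for attendance data adds a third objective to a pilot whose first task is refinement. This largely stands. It is why the main remedy is to narrow the wording, with no new endpoint. It does not dispose of the point, because clinical utility is itself part of the main phase 1 outcome.

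Several stronger readings are tempting, and the documents do not support them:

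- *That the protocol claims the Tool is safe, or that it takes the place of hospital care.* It makes no safety claim. It says the patient need not always attend, which is partial substitution. How visits are managed may be covered in the guideline, which is not available here.
- *That the study would capture nothing at all about attendance or deterioration.* The clinical list is introduced as what the data will include, so it is not strictly closed. Stage, PSA and treatments are collected, the four scored items have comment lines, and interviews could touch on attendance. None of these commits the study to a count, but they are more than nothing.
- *That the gap can be sized by how many men with worse disease would score well at a given correlation.* Any such figure needs an assumed correlation, an assumed distribution and a cut-off, and the protocol gives none of these. It would also describe the limits of correlation in general, whatever attendance data were collected.
- *That recording unplanned events would show benefit or harm.* With no comparison group and with frequency of collection left to the clinician, event counts cannot be attributed to the Tool.

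**Conclusion.** The point holds as a mismatch between conclusion and data. The rationale in 2.2 states as fact something that depends on the answer to aim 1. Section 2.3 promises a utility conclusion that the listed items and the form cannot support for home use: none of the six clinical items and none of the five office-use entries bears on place of completion, attendance or later unplanned care. Correlation with disease status and acceptability remain within reach of the design as written.

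This rests on reading the list in 2.3 and the form in 2.8 as the data to be collected, and on reading utility in the light of the home-monitoring setting that 2.3 describes. If the sponsor means by utility no more than correlation and acceptability, the rewording alone settles the matter. The two aims are unaffected. It should be settled before phase 1 data are anonymised and before the result is used to support the later phases.

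**What to change.** **Wording (no cost).**

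- In 2.2, turn the sentence into a hypothesis, for example: *If scores prove to reflect disease status, the Tool might allow some assessments to be made away from hospital, and so might lower exposure to Covid-19.*
- In 2.3, limit both the usefulness statement and the main outcome of phase 1, for example: *Phase 1 will describe how each item relates to disease status and how acceptable the Tool is to patients and clinicians. It will not establish the effect of home use on attendance or on later care.*

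**Two fields on the office-use line.**

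- *Completed at: home / clinic*
- *In place of a planned attendance: yes / no*

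Report aim 1 separately for home forms, and give the number of forms in each category. The second field relies on the clinician's judgement, and tying it to a planned attendance gives that judgement something definite to refer to.

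**Optional.** Abstract unplanned attendance, admission or death before the next clinical contact from the site's records, before anonymisation. Report these descriptively only, and state that there is no comparison group and that events at other hospitals may be missed.

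The fields mean slightly more abstraction. The optional item means more, because records must be followed from each form to the next contact. Nothing here needs a new visit or procedure, and nothing here sets a rule on who should attend or when.

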2.3 How the research will be conducted

In the light of the COVID-19 pandemic, oncologists at New Cross Hospital are advised to consider using the Tool (as per the *Oncology Interim Prostate Cancer Patient Management Guidelines* (8)) as a means of home monitoring of patients. The present project intends to provide robust evidence as to the clinical usefulness of Tool as well as insights into the drivers and barriers to its use by patients and clinicians.

This is a mixed-method study, incorporating both quantitative and qualitative elements. As such, it is both objective and subjective:

- a) It is subjective in that, in using the Wolverhampton Assessment Tool, the patient selects his response to each question on the basis of how he *feels* normally
- b) It is objective in that the tools to be used in the analysis of the quantitative data [i.e. statistical tests such as Mann Whitney-U, Spearman Rank Correlation etc.] are independent of the person using them
- c) Determining clinically the patient's disease status employs objective measures such as PSA, size, distribution and type of metastasis, frequency of night-time urination etc. as well as the clinician's professional judgment which contains both objective and subjective elements (9, 10)
- d) The researchers are not mirrors but they are rather prisms and hence the entire study from conception to analysis and report is a refraction of their experiences

The first phase of the research is a full pilot of the Wolverhampton Assessment Tool in New Cross Hospital, Wolverhampton. Patients who agree to use the Tool to self-monitor their aspects of their health will be invited to consent to share with the researchers their anonymised data from the Tool as well as linked, anonymised clinical data. The frequency of collection of data will be at the discretion of the clinician. Participating patients and clinicians will be invited to take part in a short, semi-structured interview on their experience of using the Tool. All patient data will be treated anonymously, and none linked back to the patient or to their clinician/s.

Clinicians will be asked to record any reasons given by patients who decline to use the Tool.

The clinical data sought on patients will include:

- a) Age
- b) Stage of cancer at diagnosis in terms of the primary tumour, and any presence of disease in lymph nodes and bones
- c) Current stage of cancer in terms of the primary tumour, and any presence of disease in lymph nodes and bones
- d) Level of PSA – prostate specific antigen, produced normally in the prostate but also produced in prostate cancer cells.
- e) Co-morbidities
- f) Current and previous treatments

The main outcome of the first phase will be to refine, as necessary, both the Tool and the research instruments as well as to establish proof of principle of the clinical utility of Tool.

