2.4 Later phases of the project

The second phase is to invite oncologists across the West Midlands, many of whom have already expressed an interest, to join the study and to send the researchers anonymised, linked patient data and that from the Tool.

The third phase is to make the Tool available, free of charge, as an app on both the Android Store and the Apple App Store. This will allow patients to self-monitor aspects of their health and to share this as they wish with their clinician. Users will be asked to evaluate the app by the usual means on their app store.

Clinicians who choose to use it with their patients will be asked to share with the researchers anonymised, linked patient data and that from the Tool.

The target group for this research consists of anyone being treated for advanced and metastatic prostate cancer and their clinician/s. It does not involve persons under 18 years of age nor persons from a potentially vulnerable group.

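### Barriers among non-users rest on clinician-relayed reasons for patients who decline and on no described source for clinicians who do not use the Tool

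*Protocol*

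**What the plan says.** The numbered aim in Protocol section 2.2 is to "examine patient and clinician attitudes to using the Tool", and the second research question in section 2.1 asks how both groups feel about using the Tool. Section 2.3 goes further and says that the project intends to provide "insights into the drivers and barriers to its use by patients and clinicians".

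The information is collected as follows (section 2.3):

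- Interviews: "Participating patients and clinicians will be invited to take part in a short, semi-structured interview on their experience of using the Tool".
- Study entry for patients, by agreement to data sharing: "Patients who agree to use the Tool to self-monitor their aspects of their health will be invited to consent to share with the researchers".
- Decliners: "Clinicians will be asked to record any reasons given by patients who decline to use the Tool".
- Clinicians' use is optional: "oncologists at New Cross Hospital are advised to consider using the Tool".

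Section 2.4 adds, for the app phase: "Users will be asked to evaluate the app by the usual means on their app store". Section 2.5 assigns the qualitative data to thematic analysis and the constant comparative method.

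**The concern.** A person who turns the Tool down, or a clinician who never offers it, is the most direct witness to what stops it being used. The interview excludes that person in two ways: by who is invited, and by a topic that presupposes use. The substitute for patients is thin, and for clinicians there is none.

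If the plan is followed as written, a barrier that operates before first use may never appear among the themes. Examples would be a clinician's doubt about relying on a home questionnaire, or a patient's reluctance to be monitored away from clinic. The report could then read as if such barriers did not exist. No later analysis can recover views that were never collected, so this belongs in the Protocol and cannot be left to an analysis plan.

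**Working it through.** No arithmetic applies. The Protocol states no interview number, uptake or decline rate, and the point depends on none. The check is to list each group whose barriers section 2.3 promises to describe and find the source of information on it.

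| Group | Source described | Limits |
|---|---|---|
| Patients who use the Tool and take part | Interview | None on this point; they can report difficulties as well as benefits |
| Patients who decline the Tool | Reasons recorded by clinicians | Only if the patient gives one; second-hand; no form or interview; no count of patients offered or declining |
| Clinicians who take part | Interview | None on this point |
| Clinicians who do not use the Tool | None | No invitation, form or record |

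The reasoning for each step:

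1. *Patients are filtered before interview.* A patient first agrees to use the Tool and is then invited to share data (section 2.3). Interview is a further voluntary step with its own consent (section 2.6). Decliners drop out at the first step.
2. *The topic does not reach non-users.* Even if participation were read generously, the interview is about experience of using the Tool, and a non-user has none.
3. *Non-using clinicians can exist.* Oncologists are advised only to consider the Tool, and clinicians are named alongside patients in the statement on barriers.
4. *Later phases do not fill the gap.* Phase 2 invites oncologists, many of whom are already interested. Phase 3 takes evaluation from app users and data from clinicians who choose to use the app (section 2.4).
5. *Decliners' reasons have no denominator.* Without the number offered, a short list of recorded reasons could mean few refusals or many refusals with no reason given.

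**The case against.** Four arguments on the other side deserve weight.

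- *The authors did provide for decliners.* A reader might infer that barriers are learnt from adopters alone. The instruction to record decliners' reasons contradicts this. The source is weak, but it exists, so the stronger statement fails for patients. It stands for clinicians.
- *The numbered aim and research question concern attitudes to using the Tool, and user interviews suit that wording.* This is correct. Drivers and barriers are an intention stated once in section 2.3, and uptake is not named as an outcome. The point is therefore a shortfall against that intention. It does not mean that the second research question goes unanswered.
- *Thematic analysis does not estimate how common a barrier is.* A reader might infer that user interviews will understate the frequency of barriers by some calculable amount. The Protocol plans no such estimate and gives no rates from which to work one out, so a numerical bias is not supported. What remains is the possible loss of whole themes. That patients may soften reasons given to a clinician is plausible, but the document does not establish it.
- *This is a single-hospital pilot meant to refine the Tool and the research instruments.* User experience is indeed the direct evidence for refinement. But a pilot is also the stage at which reasons for non-use can still alter the design, and no later phase is set up to collect them.

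**Conclusion.** The point holds in limited form. The described data cover barriers among users by interview, among declining patients only by volunteered and relayed reasons without a denominator, and among non-using clinicians not at all. Barriers specific to non-users may be missed.

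No numerical size can be derived from the document. The conclusion rests on two readings: that participating means taking part as a user of the Tool, which the interview topic supports, and that some clinicians will choose not to use it, which the advisory guidance allows. It does not rest on any assumed decline rate. This is an inexpensive improvement and not a flaw that undermines the study.

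**What to change.** In section 2.3, change both the invitation and the topic. Suggested wording: *Patients offered the Tool and clinicians invited to use it, whether or not they take it up, will be asked to a short semi-structured interview about either their use of the Tool or their reasons for not using it.* Changing the invitees alone would not work, because non-users would then be asked about an experience they have not had.

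Two additions:

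- As the minimum for patients who decline, an optional anonymous card for their reason, so that it need not pass through the clinician.
- A count of patients and clinicians offered the Tool, accepting and declining.

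Opt-in consent as in section 2.6 can be used, extended to people who are not otherwise in the study.

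The cost is a short alternative topic guide, an adapted information sheet and a tally. Clinical procedures do not change. Uptake among decliners will probably be low, so the gain may be modest.

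If the change is not made, the Protocol should say that conclusions on barriers apply to users, with decliners' recorded reasons reported separately and described as second-hand.
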